Target population	 Inclusion criteria Histologically confirmed prostate adenocarcinoma Clinical stage T1c-T3b, N0, M0 Gleason sum 7-10 At least 2 positive cores Prior decision to undergo radical prostatectomy Adult male ≥18 years of age ECOG performance status 0-1, or Karnofsky score ≥ 70% Adequate kidney, liver, and bone marrow function Willingness to sign informed consent and adhere to study requirements Exclusion criteria: Presence of known lymph node involvement or distant metastases Prior radiation, hormones, biologics, or chemotherapy for prostate cancer Prior use of experimental agents for prostate cancer Prior use of experimental agents for prostate cancer History of autoimmune disease requiring systemic immunosuppression History of other malignancy within 3 years Uncontrolled major infectious, cardiovascular, pulmonary, hematologic, or psychiatric illnesses that would make the patient a poor study candidate

IRB#: IRB0010377

Johns Hopkins University

Start date/Initial patients are expected to be entered in November 2016. With an estimatedDurationenrollment rate of 3 patients per month, accrual is expected to last 5-6 months.

The trial was originally designed to evaluate safety and PD endpoint with 16 patients. Based on promising PSA response data prior to prostatectomy, following Enoblituzumab therapy alone, the study will enroll an additional 16 patients for a total size of 32 – amendment 1. All patients will be enrolled utilizing identical inclusion, exclusion, and treatment conditions as the first 16 patients. Expanding the trial to enroll a total of 32 patients will provide statistical power to estimate the clinical benefit of Enoblituzumab in terms of undetectable PSA level (<0.1 ng/mL) 12 months following radical prostatectomy.

Sample size 16 evaluable patients (*i.e.* those that undergo prostatectomy)

16 additional patients in the expansion Amendment 1 will be enrolled for a total sample size of 32 patients.

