- Mean NK cell density in tumor tissue from harvested prostate glands of patients

- Proportion of treated patients with detectable Enoblituzumab in prostate tumor specimens(fresh frozen section)
- Proportion of pathological complete responses (pCR) in each treatment group
- Proportion of patients achieving a PSA response rate (PSA <0.1 ng/mL) at 3 months after prostatectomy
- Median time-to-PSA-recurrence (PSA ≥0.2 ng/mL) after radical prostatectomy
- Median PSA decrease prior to radical prostatectomy
- To assess Gleason grade change post neoadjuvant Enoblituzumab treatment, by comparing prostatectomy Gleason sum to pre-treatment biopsy Gleason sum

Statistical Our primary objective(s) is to characterize safety, tolerability, and feasibility of treatment of men with Enoblituzumab in the neoadjyuant setting as well as obtain an methods estimate of PSA₀ response rate 12 months following radical prostatectomy. The trial will monitor toxicity and safety, as well as feasibility with respect to its impact on subsequent surgery. The secondary objective will be to evaluate an anti-tumor effect consistent with the agent's proposed mechanism of action (MOA), antibody-dependent cellular cytotoxicity (ADCC). Tumor cell death will be quantified by Caspase staining, and post-treatment apoptotic index compared with that from the pre-treatment biopsy. Sample size is driven by detecting a pharmacodynamic effect of the agent based on the key secondary endpoint of tumor cell death as well as in the expansion cohort to obtain an estimate of PSA_0 response. A biologically meaningful treatment effect will be deemed to be one where the tumor cell apoptosis is two-fold higher after Enoblituzumab therapy. Previous study showed that baseline apoptosis, measured by Caspase staining, is 0.06 +/- 0.08 (Mean +/-SD) for Gleason 4 and 0.2 ± 0.2 for Gleason 3 (Kim et al 2016). Based on this data, we assume that the coefficient of variation of tumor cell death measure is 1.2 and the correlations between the measures pre- and post-treatment is moderate at 0.4, 16 subjects will provide 88% power to detect a 2-fold increase in apoptotic tumor cells after the treatment compared to baseline, using a one-sided paired t-test with significance level 0.05. Other endpoints will be exploratory in nature, and quantified using descriptive statistics.

For the expansion cohort (amendment 1):

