Our primary efficacy endpoint with 32 patients will be to estimate the clinical benefit of neoadjuvant Enoblituzumab in terms of undetectable PSA level (<0.1 ng/mL) at 12 months following radical prostatectomy. There are currently no approved neoadjuvant treatments for high risk localized prostate cancer and we believe future larger neoadjuvant trials can be better designed in high risk patients if we can estimate the benefit as per the below table showing the 90% confidence interval.

Johns Hopkins University

Observed N with undetectable PSA	Observed rate	90% CI
0	0	0% - 7.8%
1	3.1%	0.7% - 12.9%
2	6.2%	2.1% - 17.2%
3	9.4%	3.8% - 21.3%

Safety analysis Frequency, types, and grades of adverse events in each treatment group will be measured using the NCI Common Toxicity Criteria version 4.0, and will be summarized using descriptive statistics. Formal safety assessments will be performed from the time of first administration of Enoblituzumab until the 90th postoperative day.

Johns Hopkins University

TABLE OF CONTENTS

1.	OBJE	OBJECTIVES		
	1.1	Primary Objectives	16	
	1.2	Secondary Objectives	16	
	1.3	Exploratory Objectives	16	
2.	BAC	KGROUND AND RATIONALE	18	
	2.1	Disease Background	18	
	2.2	Treatment Background	19	
	2.3	Rationale	23	
3.	PAT	IENT SELECTION	25	
	3.1	Target Population	25	
	3.2	Inclusion Criteria	25	
	3.3	Exclusion Criteria	26	
	3.4	Inclusion of Minorities		
	3.5	Prohibited Concomitant Medications	27	
4.	REG	ISTRATION AND ENROLLMENT PLAN	27	
	4.1	Registration Procedure	27	
	4.2	Expected Enrollment	28	
	4.3	Study Centers	28	
	4.4	Recruitment	28	
5.	STU	DY PLAN	28	
	5.1	Overview and Schema	28	
	5.2	Screening/Pretreatment Evaluation	32	
	5.3	Treatment Visits		
	5.4	Radical Prostatectomy		
	5.5	Follow-Up Evaluations	33	
	5.6	Duration of Therapy	34	
6.	STU	DY TREATMENT	34	
	6.1	Description of Study Drug and Supplies		
	6.2	Drug Preparation	35	
7.	ADV	ERSE EVENTS AND REPORTING REQUIREMENTS	42	
	7.1	Recording and Grading	42	
	7.2	Unexpected Adverse Events	44	
	7.3	Serious Adverse Events and Serious Adverse Drug Reactions	44	
	7.4	Perioperative Adverse Events		
	7.5	Reporting Adverse Events	46	
	7.6	Pregnancy	48	
8.	OUT	COME ASSESSMENT	48	
	8.1	Radical Prostatectomy Specimen	48	
	8.2	Primary Endpoint	49	
	8.3	Secondary Endpoints	49	
9.	REG	ULATORY AND REPORTING REQUIREMENTS	53	
	9.1	Regulatory Responsibilities		
	9.2	Data Management	54	
	9.3	Study Monitoring and Quality Assurance	54	

Johns Hopkins University

10.	STATISTICAL CONSIDERATIONS	

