10.3 Analysis Populations

10.3.1 Intention-to-treat population

All patients who meet eligibility criteria and receive at least one dose of the study drug will be included in the analysis of the primary and secondary endpoints, even if there are subsequent protocol deviations. However, in cases where prostatectomy is not performed or if adequate surgical tissue is not collected, then determination of the secondary endpoints (apoptosis/proliferation marker analysis, tissue CD8⁺ T cell analysis) will not be possible. Patients will be replaced if they are removed from the study after signing the informed consent but before receiving the study drug.

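### Pre-operative PSA decrease is pooled by default over all 32 men although promising pre-operative PSA data prompted the expansion; it should also be reported by cohort.

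*Combined protocol and SAP*

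**What the plan says.** The Synopsis (Start date/Duration) gives the history: "The trial was originally designed to evaluate safety and PD endpoint with 16 patients". It then gives the reason for growth: "Based on promising PSA response data prior to prostatectomy, following Enoblituzumab therapy alone, the study will enroll an additional 16 patients". The Sample size entry confirms the total: "16 additional patients in the expansion Amendment 1 will be enrolled for a total sample size of 32 patients". The two groups are meant to be alike: "All patients will be enrolled utilizing identical inclusion, exclusion, and treatment conditions as the first 16 patients".

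The Synopsis list of secondary endpoints includes "Median PSA decrease prior to radical prostatectomy", with no cohort named. The summary of changes for Amendment 1 lists the same item under the criteria for evaluation, so the endpoint entered with the expansion.

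Section 10.3.1 states that eligible men who receive at least one dose "will be included in the analysis of the primary and secondary endpoints, even if there are subsequent protocol deviations". Section 5.6 limits efficacy analyses to men who also have prostatectomy. Neither section separates the first 16 from the expansion 16. Sections 8.3 and 10.2.2 have no entry for pre-operative PSA decrease. The plan states no expansion threshold, no count of men whose PSA results were reviewed, and no adjustment for the data-driven decision.

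The Synopsis (Statistical methods) says of endpoints beyond the powered one: "Other endpoints will be exploratory in nature, and quantified using descriptive statistics".

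**The concern.** When a trial continues because an early result looks good, the early result is, on average, better than the truth. Pooling it with later data dilutes the excess but does not remove it. Here the early result was pre-operative PSA, and pre-operative PSA decrease is itself a reported endpoint. A pooled median over 32 men would carry part of the excess, and its interval would not show it.

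Identical eligibility and treatment do not cure this, because the selection acts on the observed results of the first men and not on who was enrolled. The same identity of conditions makes the expansion 16 a clean replication. At stake is how large a pre-operative PSA effect readers take from the trial.

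**Working it through.** **The plan's own figures.** No figure is stated for pre-operative PSA decrease. The nearest stated precision figures are the 90% intervals for 12-month PSA0 in Section 10.2.1.1. They reproduce as Wilson intervals with n = 32. For 1 responder, p = 0.03125 and z = 1.645:
- centre = (0.03125 + 2.706/64)/(1 + 2.706/32) = 0.068
- half-width = 1.645 × √(0.03125 × 0.96875/32 + 2.706/4096)/1.0846 = 0.061
- interval = 0.7% to 12.9%, as printed

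The other rows also match (0–7.8%, 2.1–17.2%, 3.8–21.3%). PSA0 is therefore planned on all 32.

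**Inputs from the documents.** There are 16 + 16 men under the same conditions (Synopsis). Pre-operative PSA is scheduled only before treatment and on the day of surgery (Table 1, footnote e).

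**Assumptions.** Individual PSA changes are normal with SD 1, so bias is in SD units. Expansion occurs only if the first-16 estimate passes a threshold c (in standard errors above the truth). The prior chance of expansion, P, runs from 90% to 10%.

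**Check by formula, for a mean.** The first-16 mean has standard error 1/√16 = 0.25 SD. Given expansion, its bias is λ/4 with λ = φ(c)/P, and the pooled bias is half of that, λ/8. At P = 50%, c = 0 and λ = 0.3989/0.5 = 0.798. The first-16 bias is 0.798/4 = 0.20 SD and the pooled bias is 0.10 SD. The pooled standard error is 1/√32 = 0.177 SD.

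**The endpoint itself, a median.** Simulation of 200,000 trials, with expansion only if the first-16 median passes the threshold. The sampling SD of the 32-man median is 0.216 SD.

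| Prior chance of expansion | Bias, first 16 | Bias, expansion 16 | Bias, pooled 32 | Pooled bias / 0.216 |
|---|---|---|---|---|
| 90% | 0.06 | 0.00 | 0.03 | 0.13 |
| 75% | 0.13 | 0.00 | 0.06 | 0.29 |
| 50% | 0.24 | 0.00 | 0.12 | 0.54 |
| 25% | 0.38 | 0.00 | 0.18 | 0.85 |
| 10% | 0.53 | 0.00 | 0.24 | 1.12 |

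**If fewer men had contributed.** With 8 men and P = 50%, the pooled-mean bias is (0.798/√8) × (8/32) = 0.07 SD instead of 0.10.

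**Total error, for a mean.** Given expansion, E[Z²] = 1 + cλ, so the pooled mean squared error is (2 + cλ)/64. For the expansion 16 alone it is 1/16 = 0.063.
- c = 0 (P = 50%): 2/64 = 0.031, so pooled is better.
- c = 1 (P about 16%, λ = 1.525): 3.525/64 = 0.055, so pooled is still better.
- c = 1.28 (P = 10%, λ = 1.755): (2 + 2.249)/64 = 0.066, so pooled is slightly worse.

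Simulated medians show the same ordering in the first two cases: 0.047 against 0.090, and 0.082 against about 0.09.

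**Cost in precision.** The 16-man interval is wider by √(32/16) = 1.41.

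**The case against.** The strongest reply is that the link is inferred. The expansion text speaks only of promising PSA response data, with no definition and no count. Sections 8.3.17 and 10.2.2 use PSA response for an undetectable value after surgery, which cannot have been the trigger. This stands as a limit. The only scheduled pre-operative PSA values are the two behind this endpoint, so the reading is close, but it is not stated. The endpoint's place in the summary of changes, below the expansion heading, might mean it was intended for the expansion cohort only; the current Synopsis does not say so.

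Second, if expansion was likely from the start, the bias is small: 0.03 to 0.06 SD at a 90% to 75% chance. That is correct, and the range must include it. The bias is also conditional on expanding. Averaged over all hypothetical trials, including those that stop at 16, it is slightly negative (−0.03 to −0.06 SD). Since the expansion was adopted, the conditional figure is the relevant one.

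Third, the expansion 16 alone give up accuracy for freedom from selection. Unless expansion was very unlikely, the pooled value has the smaller total error. This stands, and it is why the pooled value should be kept.

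Fourth, no test and no type I error are involved, and the reason for expansion is disclosed. This limits the point to a minor one.

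A reader might infer that the next trial would be undersized as a direct result. The documents do not support that. The Synopsis ties future trial design to the 12-month PSA0 rate ("Our primary efficacy endpoint with 32 patients"), not to pre-operative decrease.

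A reader might also infer that PSA0 is materially overstated. Any bias there works only through its correlation with pre-operative decline. Assuming a 70% true rate, a latent correlation of 0.2 to 0.4 and a 25% to 50% chance of expansion gives about 0.6 to 1.8 points, and zero correlation gives none. The documents supply none of these inputs, so the PSA0 bias cannot be sized from them.

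**Conclusion.** The point holds in a limited form. If the pre-operative PSA changes that prompted expansion are those feeding this endpoint, the pooled median is biased upward given expansion. The size is about 0.03 to 0.24 SD over an assumed 90% to 10% chance of expansion, or roughly 0.1 to 1.1 times the sampling SD of the pooled median. The expansion 16 are free of this bias. The direction follows from the documents under that reading. The size does not, because no threshold, SD or number of contributing men is given. The consequence is a possibly optimistic description of one secondary endpoint, not a flaw in the primary analyses.

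**What to change.** In Section 10.2.2, add an entry for median pre-operative PSA decrease, with a matching definition in Section 8.3. Report the median with its interval for the first 16, the expansion 16 and all 32 side by side. Identify the expansion-16 value as the one not subject to selection, and label the pooled value as including the data that prompted expansion.

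Keep n = 32 for PSA0; a split by cohort there is optional.

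The cost is a paragraph of text and extra table columns, with no new patients, visits or assays. The drawback is that the 16-man interval is about 1.4 times as wide as the pooled one. The pooled value can still have the smaller total error, so it should remain in the table.

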	 10.1 Study Design and Sample Size 10.2 Study Endpoints	
	10.2 Study Endpoints	
	10.4 Safety Analysis	
11.	PROTECTION OF HUMAN SUBJECTS	60
	11.1 Ethical Considerations	60
	11.2 Protocol Amendments	60
	11.3 Written Informed Consent	60
	11.4 Protection of Privacy	61
	 11.6 Protection of Privacy 11.5 Study Termination or Modification 	61
12.	REFERENCES	
APPE	ENDIX A: PERFORMANCE STATUS CRITERIA	
APPE	ENDIX B: COMMON TOXICITY CRITERIA, VERSION 4.0	
APPE	ENDIX C: SERIOUS ADVERSE EVENT (SAE) REPORTING FORM	
APPE	ENDIX D: ABBREVIATIONS AND ACRONYMS	
APPE	ENDIX E: DATA AND SAFETY MONITORING PLAN (DSMP)	72 2
APPE	ENDIX F: SPECIMEN COLLECTION AND SHIPPING	

LIST OF TABLES

Table 1	Study Calendars	21
Table 2	Intensity of Adverse Event	32
Table 3	Relationship of Adverse Event to Study Drug	32
LIST OF F	IGURES	
Figure 1	Clinical States of Prostate Cancer	10
Figure 2	MGA271 (RES242) Mediates ADCC Activity Across a Spectrum of Cancer Types	13
Figure 3	Study Schema	20

Summary of changes for Protocol Amendment 1 version 1.5:

The trial was originally designed to evaluate safety and PD endpoint with 16 patients. Based on promising PSA response data prior to prostatectomy, following Enoblituzumab therapy alone, the study will enroll an additional 16 patients for a total size of 32 – Amendment 1.

All patients will be enrolled utilizing identical inclusion, exclusion, and treatment conditions as the first 16 patients. Expanding the trial to enroll a total of 32 patients will provide statistical power to estimate the clinical benefit of Enoblituzumab in terms of undetectable PSA level (<0.1 ng/mL) 12 months following radical prostatectomy.

IRB#: IRB0010377

Section	Changes:
Synopsis	Start date/ Duration:
	The trial was originally designed to evaluate safety and PD endpoint
	with 16 patients. Based on promising PSA response data prior to
	prostatectomy, following Enoblituzumab therapy alone, the study will
	enroll an additional 16 patients for a total size of 32 – amendment 1. All
	patients will be enrolled utilizing identical inclusion, exclusion, and
	treatment conditions as the first 16 patients. Expanding the trial to
	enroll a total of 32 patients will provide statistical power to estimate
	the clinical benefit of Enoblituzumab in terms of undetectable PSA level
	(<0.1 ng/mL) 12 months following radical prostatectomy.
	Sample size:
	16 additional patients in the expansion Amendment 1 will be enrolled
	for a total sample size of 32 patients.
	Objectives:
	Primary: In the expansion cohort (Amendment 1):
	 PSA₀ Response (Undetectable PSA level <0.1 ng/mL) at 12 months
	following radical prostatectomy.
	Secondary:
	 To assess Gleason grade change post neoadjuvant Enoblituzumab
	treatment, by comparing prostatectomy Gleason sum to pre-treatment
	biopsy Gleason sum
	•To quantify the extent of PD-L1+ cell density in the prostate from
	harvested prostate glands of treated patients.
	Criteria for evaluation:
	In expansion (Amendment 1):
	•PSA ₀ Response (Undetectable PSA level <0.1 ng/mL) at 12 months
	following radical prostatectomy
	Median PSA decrease prior to radical prostatectomy
	•To assess Gleason grade change post neoadjuvant Enoblituzumab
	treatment, by comparing prostatectomy Gleason sum to pre-treatment
	biopsy Gleason sum
	Statistical methods:
	For the expansion cohort (amendment 1):
	Our primary efficacy endpoint with 32 patients will be to estimate the
	clinical benefit of neoadjuvant Enoblituzumab in terms of undetectable
	PSA level (<0.1 ng/mL) at 12 months following radical prostatectomy.
	There are currently no approved neoadjuvant treatments for high risk
	localized prostate cancer and we believe future larger neoadjuvant

	trials can be better designed in high risk patients if we can estimate the				
	benefit as per the below table showing the 90% confidence interval.				
	Observed N with undetectable PSA Observed rate 90% Cl				
	0 0 0% - 7.8%				
	1 3.1% 0.7% - 12.9%				
	2 6.2% 2.1% - 17.2%				
	3 9.4% 3.8% - 21.3%				
1.1 Primary Objectives	In expansion cohort (amendment 1):				
	•To estimate PSA ₀ Response Rate (Undetectable PSA level <0.1 ng/mL)				
	at 12 months following radical prostatectomy				
1.2 Secondary Objectives	•To quantify the extent of PD-L1+ cell density in the prostate from				
	harvested prostate glands of treated patients.				
	•To quantify the extent of NK cell infiltration into the prostate from				
	harvested prostate glands of treated patients.				
	• Enoblituzumab (MGA271) intraprostatic drug distribution in treated				
	patients.				
	• To assess Gleason grade change post neoadjuvant Enoblituzumab				
	treatment, comparing prostatectomy Gleason sum to pre-treatment				
	biopsy Gleason sum				
1.3 Exploratory Objectives	•IHC analyses of CD137, CD16 and/or CD107A across potential immune				
	infiltrate following Enoblituzumab (based on proposed MoA)				
	•Tissue androgen concentrations				
	Androgen receptor (AR) quantification				
	•Global expression profiling of pre and post treatment tumor tissue				
	using single cell RNA sequencing, the immune NanoString immunopanel				
	and/or Affy microarrays				
Table 1 Study Calendar	Footnote C: These labs should be collected prior to treatment.				
8.2.2 In expansion cohort	•All subjects receiving at least one dose of the study drug will be				
(amendment 1)	assessed for PSA ₀ Response Rate (Undetectable PSA level <0.1 ng/mL)				
	at 12 months following radical prostatectomy				
8.3.4 PD-L1 expression	PD-L1 expression in prostate tumor specimens will be assessed by IHC				
	be expressed as the mean staining percentage of PD-L1 in tumor tissue.				
8.3.7					
	•				
	as the mean staining percentage in tumor tissue.				
8.3.19	In expansion cohort (Amendment 1): assessment of Gleason grade				
	change (prostatectomy Gleason sum vs. core biopsy Gleason sum) post				
	neoadjuvant Enoblituzumab treatment				
8.3.7	 in the primary core specimens (pre-treatment) and in the prostatectomy surgical specimens (post-treatment). This endpoint will be expressed as the mean staining percentage of PD-L1 in tumor tissue. Mean NK cell density in tumor tissue from harvested prostate glands of patients. The method for quantifying NK cell density from harvested prostate tissue is as described in Section 8.3.3. This endpoint will be expressed as the mean staining percentage in tumor tissue. In expansion cohort (Amendment 1): assessment of Gleason grade change (prostatectomy Gleason sum vs. core biopsy Gleason sum) post 				

	This will be defined by comparing highest Gleason grade from pre- treatment biopsy versus highest Gleason grade from post-treatment prostatectomy. This endpoint will be expressed as the proportion of men achieving a Gleason score change.			
8.3.20	Global expression profiling of pre and post treatment tumor tissue using single cell RNA sequencing, the immune NanoString immunopanel and/or microarrays Expression profiling will be conducted as per established protocols for single cell RNA seq, Nanostring, and microarray			
8.3.21	IHC analyses of CD137, CD16 and/or CD107A across potential immune infiltrate following Enoblituzumab CD137, CD107A, and CD16 expression in prostate tumor specimens will be assessed by IHC in the prostatectomy surgical specimens (post- treatment). This endpoint will be expressed as the mean staining percentage of each of these in in tumor tissue.			
10.1 Study Design and Sample Size	In Amendment 1, the study was expended to enroll an additional 16 patients for a total of 32 patients to continue evaluating safety and better estimate the clinical benefit of Enoblituzumab in terms of undetectable PSA level (<0.1 ng/mL) at 12 months following radical			
10.2 Stopping rules	prostatectomy.Not feasible if the observed number of surgical complications is:23456In number of patients between: 2 - 67 - 1415 - 2223 - 3031 - 32The operating characteristics of the first 3stopping rule are shown below and are based on 5000 simulations:Risk of surgical complication0.0250.050.100.150.20% of Time study stops1.1%5.9%29.2%57.7%81.4%Expected sample size31.730.726.420.915.3			
10.2.1.1 For expansion Amendment 1	Estimation of PSA ₀ Response Rate (Undetectable PSA level <0.1 ng/mL) at 12 months following radical prostatectomy. Our primary efficacy endpoint will be to estimate the clinical benefit of neoadjuvant Enoblituzumab in terms of undetectable PSA level (<0.1 ng/mL) at 12 months following radical prostatectomy. The estimate and corresponding 90% confidence interval based on 32 patients have complications is listed in the table below. Observed N with undetectable PSA 0 0 0% - 7.8% 1 3.1% 0.7% - 12.9% 2 6.2% 2.1% - 17.2%			

IRB#: IRB0010377

Johns Hopkins University

	3 9.4% 3.8% - 21.3%
10.2.2 Analysis of the secondary and exploratory endpoints	 PD-L1+ cell density. The methods for quantifying and analyzing PD-L1 cell density will be similar to those described for CD8+ T cell infiltration. Descriptive statistics and graphical summaries will be provided Mean NK cell density. The methods for quantifying and analyzing NK cell infiltration will be similar to those described for CD8+ T cell infiltration. Descriptive statistics and graphical summaries will be provided Mean NK cell density. The methods for quantifying and analyzing NK cell infiltration. Descriptive statistics and graphical summaries will be provided. Enoblituzumab (MGA271) drug distribution. Intraprostatic Enoblituzumab staining concentrations will be summarized descriptively. Gleason grade change post neoadjuvant Enoblituzumab treatment from pre-treatment biopsy. This will be calculated utilizing the highest Gleason grade from the pre-treatment biopsy and the post-treatment
	prostatectomy.
APPENDIX F	 Sera for Immunoassays : Please Ping "Vaccine Team" ([contact]) and the Immune Core will be notified to pick up the sample after draw. Peripheral blood lymphocytes (PBLs): Please Ping "Vaccine Team" ([contact]) and the Immune Core will be notified to pick up the sample after draw.

IRB#: IRB0010377

1. **OBJECTIVES**

